Assessment by Ultrasound of the degree
of venous dilatation, comparison
between venodilation by Airglove™
versus Warm Water Immersion (WWI)

HLS/PSAWAHS/18/168

25th March 2019

Title: Assessment by Ultrasound of the degree of venous dilatation, comparison between venodilation by Airglove™ versus Warm Water Immersion (WWI)

Researcher: [name] [contact],

Supervisors: [name], [name] [name]

Background Information:

Failure to cannulate to gain intra-venous access is a common occurrence in patients undergoing chemotherapy, obese patients, intravenous drug users and those with chronic medical problems leading to peripheral venous collapse. Difficulty in gaining IV-access is a serious medical consequence since important life-saving drugs, fluids, blood transfusions, and other medication are usually given via the intravenous route. Most chemotherapy units in the UK rely on venous dilation by immersing the forearm of patients with “difficult to cannulate veins” (DTCV) into a bucket of warm water. There are however, limitations in this method such as controlling water temperature and ensuring proper sterility.

A new device Airglove™ has been developed which directs warm air over the forearm in a polythene sleeve causing venodilation. Preliminary studies in chemotherapy patients suggest that the Airglove™ causes venodilation to the extent of the warm water immersion technique, however further evidence is required with testing on normal healthy volunteers.

Aims and Objectives:

To determine whether Airglove™ warming device dilates upper limb veins to the same degree as the warm water immersion (WWI) method.

Participants and Recruitment Methods:

Students and staff (n=30) from the School of Health and Life Sciences, who fit the inclusion/exclusion criteria, will be invited via email to take part in this non-invasive study. A participant information letter and consent form have been drawn up to ensure appropriate informed consent is obtained. Details of gatekeeper access authorisation and a recruitment email are included with this application.

Inclusion Criteria:

- * Participants > 18 years old
- * Able to give written informed consent
- * Able to understand and complete questionnaire forms independently

Exclusion Criteria:

- * Participants < 18 years old
- * Participants with cancer and/or undergoing chemotherapy
- * Participants with difficult to cannulate veins (DTCV)
- * Participants with lymphoedema in either hand
- * Participants with pre-existing Raynaud's disease
- * Participants with Diabetes (Type 1 & 2)
- * Participants with generalised anxiety disorder
- * Participants with diagnosis of hypertension
- * Participants with any cardiovascular disease, previous stroke, episodes of DVT, recent treatment for venous thromboembolism (VTE), recently administered heparin, participants on warfarin or any anticoagulant treatment (including NOACs).
- * Participants not able to give written informed consent
- * Participants not able to comprehend or complete questionnaire forms independently

Design and Methods:

A prospective comparative study will take place in one of the ward areas of the Govan Mbeki Building, GCU Glasgow campus. Participants will expect to give up approximately 50 minutes to take part in the study. No payment or incentive will be offered.

Procedure:

- Anonymised participant demographic (age, gender, height, weight, body fat percentage, basal temperature and hydration status) data will be recorded electronically.
- Participants will be placed in a semi-recumbent position, while measurements are taken of the both arms. Blood pressure measurements will also be taken.
- Baseline 2D ultrasound long and short axis measurements of the dorsal metacarpal vein at the wrist and cephalic and median cubital veins of the cubital fossa will be taken.

Airglove™ Method Assessment:

- Select temperature setting at 38.5°C. Gently slide plastic sleeve onto RIGHT arm of volunteer, start machine. Airglove will warm the air for 3 minutes and will automatically stop.
- Discard the plastic sleeve and dispose of this as per GCU practice for recyclable plastics policy. (Sleeve is single use only).
- Carry out ultrasound examination of all 3 veins and record vein dimensions.
- Allow participants to rest 10 minutes before crossing to WWI method.

Warm Water Immersion Method Assessment:

- Collect warm water (from tap) into a bucket. Adjust the temperature of the water to 38.5° using titration of cold water
- Immerse entire RIGHT forearm of the volunteer into the bucket for 3 minutes. Remove arm and pat dry with appropriate towelling.
- Carry out ultrasound examination of all 3 veins and record the vein dimensions.

Repeat Airglove and warm water immersion procedures for participants LEFT arm.

Anonymised participant demographic data will be recorded and stored electronically and held as double password protected electronic file for analysis. Data will be confidential and anonymised at point of collection. Only the research team will have access to the data.

Anonymised ultrasound data will be recorded electronically within the equipment hard-ware – accessible via security system log in. Data will be transferred and held as double protected electronic file for analyses. Data will be confidential and anonymised at point of collection.

Electronic data will be stored securely at Glasgow Caledonian University for 7 years (end of project + 6 years in compliance with GCU Research Innovation and Enterprise record retention schedule, 2016).

Consent, confidentiality and anonymity: Participants will be provided with a participant information document to read prior to commencing the study. After coming into the study room participants have the opportunity to review the participant information document with a research team member and will have the opportunity to ask any questions or raise any concerns regarding their participation. Participation is entirely voluntary and participants may withdraw at any point. Following participant consent, participants will be allocated an ID number to ensure anonymity. Confidentiality will be maintained as only members of the research team will have access to the data with identifiable information. This data will be stored on a University owned and password protected computer. All data will be coded to ensure anonymity.

Risk to participants/self: There are no significant potential risks, psychological or physical, to participants foreseen in this study. Participants will be informed of all testing procedures beforehand and made aware of any potentially uncomfortable aspects. Light pressure will be applied to the skin surface of the forearm, however it is considered that there is no significant risk to participants.

Arrangements for debriefing: Following data collection, participants will be thanked for their participation and debriefed on the procedure completed. They will be given an opportunity to provide contact information if they wish to be informed of the results of the overall study and/or subsequent publications. Further, in the unlikely event that an unexpected finding occurs (e.g. detection of high blood pressure) the participant will be notified and results reported to the participants General Practitioner.

Statement of ethical considerations raised: All participants will be fully informed with consent prior to any data collection activities. No ethical considerations raised.

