**Assessment by Ultrasound of the
degree of venous dilatation,
comparison between venodilation
by Airglove™ versus Warm Water
Immersion (WWI)**

HLS/PSAWAHS/18/168

30th April 2019

Statistical analysis and sample size calculations

This study enrolled 34 participants, a minimum sample size of 24 was required for 90% power, $\alpha = 0.05$ and the ideal anticipated Cohen's "d" effect size of 0.833, calculated using the "pwr.T.test" module in R version 3.60 ^{9 10}. Mean venodilation by WWI and AirGloveTM for input into the "pwr.T.test" script was determined from previous pilot studies carried out at the Sir Geraint Evans Wales Heart Research Institute, Cardiff. All statistical analysis was carried out with SPSS ver.25 (IBM Corp), SciPy module (ver 1.3) for Python (ver 3.7.2) and R version 3.60 with $P<0.05$ considered as statistically significant.

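### The only stated aim asks whether Airglove and warm water dilate veins equally, but the SAP offers only a difference-test sample size and a P<0.05 threshold, so it has no rule for answering yes

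*Protocol*

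**What the plan says.** **Aim.** Under Aims and Objectives the Protocol gives a single aim, to determine whether the Airglove "dilates upper limb veins to the same degree as the warm water immersion (WWI) method". Its Background Information is also worded as similarity: preliminary work in chemotherapy patients is said to suggest that the device "causes venodilation to the extent of the warm water immersion technique".

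**Design.** Design and Methods begins "A prospective comparative study will take place", and the title also uses the word comparison. Each participant has both methods on the right arm. The next instruction is "Repeat Airglove and warm water immersion procedures for participants LEFT arm". Baseline work is described as "Baseline 2D ultrasound long and short axis measurements of the dorsal metacarpal vein" and of two veins at the elbow. After each method the instruction is to scan all three veins again, for example "Carry out ultrasound examination of all 3 veins and record the vein dimensions". No vein, arm or dimension is named as primary.

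**Analysis.** The Protocol has no analysis section. The SAP is one paragraph. It says "This study enrolled 34 participants" and that at least 24 were needed for 90% power at alpha 0.05 with an anticipated Cohen's d of 0.833. It refers to pilot means for the two methods, lists software, and sets P<0.05 as the threshold for significance. It states no hypothesis, names no test for the outcome, and gives no margin, equivalence procedure or CI rule.

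**The concern.** The aim has two possible answers: the methods dilate veins equally, or they do not. A significance threshold applied to a test for a difference can deliver only the second. A non-significant result means that zero difference has not been excluded. It does not mean that differences large enough to matter have been excluded. To support the first answer, the plan would have to say how large a difference may be and still count as the same, and require the data to rule out anything larger.

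The conclusion of the study is at stake. The Protocol says that most UK chemotherapy units rely on warm water immersion for difficult veins. A report that the new device matches it, resting only on P>=0.05, would have no support in this plan.

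**Working it through.** **Inputs from the documents.** Enrolled n = 34, required n = 24, power 90%, alpha 0.05, d = 0.833 (all SAP). Both methods are applied to the same participants (Protocol, Procedure).

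**Assumptions, not in the documents.** Paired two-sided 5% t-test; one value per participant; all 34 analysable; unit = SD of the paired differences. That SD is not given, so nothing below converts to vein dimensions.

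**1. The plan's own figure.** Noncentral-t sample sizes for d = 0.833 and 90% power are:

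| Test | n |
|---|---|
| Paired, two-sided | 18 |
| Paired, one-sided | 14 |
| Two-sample, two-sided | 32 per group |
| Two-sample, one-sided | 26 per group |

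None gives exactly 24. A two-sample two-sided test at 80% power does (24 per group). Which calculation was run is a separate question. What matters here is that every one of these is a test for a difference. The 0.833 cannot be read as a margin either, because the SAP calls it an anticipated effect size and mentions pilot means for each method as input.

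**2. How often a real difference gives P>=0.05 at n = 34.** The noncentrality is δ√34 = 5.831δ, df = 33, and the critical value is t(0.975, 33) = 2.035. P(P>=0.05) is the noncentral-t probability between −2.035 and 2.035.

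| True difference δ (SD) | Noncentrality | P(P>=0.05) |
|---|---|---|
| 0.4 | 2.33 | 38% |
| 0.5 | 2.92 | 19% |
| 0.6 | 3.50 | 8% |

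**3. Precision.** The 95% CI half-width is 2.035/√34 = 0.349 SD. The 90% half-width is 1.692/√34 = 0.290 SD.

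**4. What a non-significant result leaves open.** This depends on the observed interval. With a half-width of 0.35, an observed difference below about 0.40 − 0.35 = 0.05 SD excludes 0.4 SD, and one below about 0.50 − 0.35 = 0.15 SD excludes 0.5 SD. In simulation with zero true difference, 74% of non-significant results had a 95% CI reaching 0.4 SD in one direction or the other, and 35% had one reaching 0.5 SD.

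**5. What a sameness rule could achieve.** The rule is to claim sameness within a margin M if |mean difference| + 1.692·s/√34 < M, that is, if the 90% CI lies inside ±M. The margins are assumed and the true difference is zero. Power for **a single endpoint**, integrated over the sample SD:

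| Margin (SD) | Power |
|---|---|
| 0.4 | 48% |
| 0.5 | 77% |
| 0.58 | 90% |

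If no primary is chosen and every CI must lie inside the margin, power falls. Three veins × two arms = 6 endpoints; with two axes, 12. The Protocol specifies both axes only at baseline. At M = 0.58 SD, simulated power is about 54–75% for six endpoints and 29–67% for twelve, for assumed correlations of 0 to 0.8. As a check on the independent case, 0.904^6 ≈ 0.55 and 0.904^12 ≈ 0.30, within simulation error of the lower ends.

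**The case against.** The strongest reply is that this is a difference study whose aim is loosely worded. The title and the design statement both speak of comparison, and the sample size rests on an anticipated difference. On that reading, asking whether the device dilates veins to an equal degree is plain language for testing whether it does not. Harm follows only if P>=0.05 occurs and is then misread. This reading is plausible, and it is why one remedy is simply to restate the aim. It does not remove the mismatch, because as written the aim asks about sameness and the plan cannot support it.

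It can also be said that the difference test is not weak: under the stated assumptions, power at 0.5 SD is 100% − 19% = 81%. That is right, and the point is not that the study is too small. A CI could also be computed afterwards. It could, but without a margin set blind to the results a sameness conclusion from it would be post hoc, and the SAP already describes enrolment in the past tense.

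A reader might infer that any P>=0.05 here leaves differences of 0.4 to 0.5 SD plausible. That goes too far, as step 4 shows: the observed interval decides. A reader might also take the 90% power at a 0.58 SD margin as the power for a general claim of sameness. It applies to one endpoint only, and the documents name no primary.

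**Conclusion.** The point stands as a mismatch between aim and analysis. The only stated aim asks about sameness, and the only decision rule can establish a difference but not its absence. That follows from reading the two documents and needs no assumption.

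The size does rest on assumptions: a paired two-sided 5% test, one value per participant, and 34 analysable. On these, true differences of 0.4, 0.5 and 0.6 SD would be missed in 38%, 19% and 8% of studies. Whether such differences matter clinically cannot be judged, because the documents give neither an SD nor a margin.

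A reader might infer that the sponsor has claimed equivalence, or that an equivalence analysis is obligatory. The documents show neither. The fixed sequence ("Allow participants to rest 10 minutes before crossing to WWI method") might also tempt a reader to quantify an order effect. The documents give no size or direction for one, and it is a separate issue.

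This should be fixed. It is not fatal, because a difference question may have been intended and the remedy lies mainly in how the results are reported.

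**What to change.** 1. Report the paired mean difference (Airglove minus warm water immersion) with its CI. Do this for one primary vein dimension chosen without sight of the results, or otherwise for all of them.
2. Make no claim of sameness from P>=0.05.
3. Choose one of two routes. Either restate the aim as a difference or estimation question, which matches the basis of the sample size. Or claim sameness only if the 90% CI lies wholly inside a margin justified on clinical grounds in vein-dimension units, labelled post hoc if the margin was not set blind to the results.
4. State that the sample size of 24 was for detecting a difference. If equivalence power is quoted, say that it is for a single endpoint, and give the lower figure if every CI must fall inside the margin.
5. Add one line of caution that, as listed, Airglove precedes warm water on each arm.

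The cost is SAP and report wording plus a CI analysis of the recorded data. The conclusion may be less favourable, and a margin set now may carry only post hoc weight.

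### Post-warming vein dimensions are read unmasked, straight after a visible method and in a fixed order; reading coded images in random order would protect the caliper step

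*Protocol*

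**What the plan says.** In the Protocol's Procedure, baseline ultrasound of three veins, in long and short axis, comes before either method. Each method's sequence then ends with its own scan. Under Airglove Method Assessment, once the sleeve has been discarded, the step is "Carry out ultrasound examination of all 3 veins and record vein dimensions". Under Warm Water Immersion Method Assessment, once the arm has been dried, it is "Carry out ultrasound examination of all 3 veins and record the vein dimensions". The order is the same for everyone: "Allow participants to rest 10 minutes before crossing to WWI method". Both methods are then repeated on the left arm.

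On data handling, the Protocol says "Anonymised ultrasound data will be recorded electronically within the equipment hard-ware" and "Data will be transferred and held as double protected electronic file for analyses". It does not say whether these data are images, clips or only measured values. The section on consent, confidentiality and anonymity adds "All data will be coded to ensure anonymity".

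Neither document mentions masking of the reader, an independent reader, reading order, repeat readings or observer agreement. Neither says who applies the method or who scans.

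**The concern.** The outcome depends on where a person places calipers on a small vein. For every post-warming value, the plan has that done just after a sleeve or a bucket has been used, at a known point in a fixed sequence. Nothing keeps the method from the reader.

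The documents also hold expectations that a reader could share. The Background states: "Preliminary studies in chemotherapy patients suggest that the Airglove™ causes venodilation to the extent of the warm water immersion technique". The SAP, by contrast, sizes the study on an anticipated standardised effect of 0.833. A reader could therefore lean towards similarity or towards a difference.

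The within-person design cancels any over-reading common to both warmed scans. It does not cancel a preference that differs between the methods, which is added directly to the comparison of interest. A larger sample only makes such a bias more likely to reach significance. In the other direction, a bias towards equality could hide a real difference, and a non-significant result might then be taken as support for equal dilation, which is what the study aims to assess.

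**Working it through.** **Inputs from the documents**
- 34 participants enrolled, minimum 24, 90% power, alpha 0.05, d = 0.833 (SAP).
- Two arms, three veins, two axes, and three occasions per arm: baseline, after Airglove, after WWI (Protocol, Procedure).

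**Assumptions, because the documents give no figure**
- A paired two-sided t-test with one Airglove-minus-WWI difference per participant. The SAP states neither the test type nor the sidedness.
- d = 0.833 is taken in units of the SD of the within-person difference.
- Reading bias is a constant *b* in the same units, shown for 0.1, 0.2 and 0.3, with 0.5 as an extreme.

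**The plan's own figure.** At d = 0.833 and 90% power, a paired two-sided test needs 18 participants and a two-sample two-sided test needs 32 per group. The stated 24 is the two-sample two-sided answer at 80% power (80.7%); in a paired two-sided test it gives 97.4%. The basis of the 24 is a separate matter, and this point does not depend on it.

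**False positives when there is no true difference.** The test statistic is noncentral t with n − 1 degrees of freedom and noncentrality b√n. For n = 34, √34 = 5.831 and the critical value on 33 df is 2.035. The rejection probability is P(T > 2.035) + P(T < −2.035).

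| Bias b | Noncentrality, n = 34 | False positives, n = 34 | False positives, n = 24 |
|---|---|---|---|
| 0 | 0 | 5% | 5% |
| 0.1 | 0.583 | 8.7% | 7.6% |
| 0.2 | 1.166 | 20.5% | 15.6% |
| 0.3 | 1.749 | 39.7% | 29.1% |
| 0.5 | 2.915 | 80.8% | 65.0% |

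At every bias shown, the error is higher with 34 participants than with 24.

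**Power when the bias pulls towards equality.** The noncentrality becomes (0.833 − b)√34.

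| Bias b | Noncentrality | Power, n = 34 |
|---|---|---|
| 0 | 0.833 × 5.831 = 4.857 | 99.7% |
| 0.1 | 0.733 × 5.831 = 4.274 | 98.6% |
| 0.2 | 0.633 × 5.831 = 3.691 | 94.8% |
| 0.3 | 0.533 × 5.831 = 3.108 | 85.5% |
| 0.5 | 0.333 × 5.831 = 1.942 | 47.0% |

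**Offline reading load.** 34 × 2 arms × 3 occasions × 3 veins × 2 axes = 1,224 readings. For one primary vein and one axis, 34 × 2 × 3 = 204.

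**The case against.** Several stronger readings are tempting, and the documents do not support them.

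- *The person who applied the method also takes the reading.* A reader might infer this from the run of steps and from the single researcher listed on the title page. No operator is named, several supervisors are listed, and the Protocol speaks of a research team. The point needs only a reader who can know the method, and no step prevents that.
- *Every value is read with knowledge of the method.* Baseline scans come before either method, so this applies only to the post-warming scans.
- *Stored images are available for re-reading.* The Protocol refers to ultrasound data. If only measured values were kept, re-reading is impossible; if only caliper-marked frames were kept, it is compromised. The SAP reports enrolment in the past tense, so this may decide whether anything can still be done.
- *The flaw is fatal to a claim of equal dilation.* Only differential bias survives pairing, and its size is unknown. The one expectation about the comparison put into words is similarity, and under a bias in that direction of up to 0.3 SD, power at d = 0.833 stays at 85.5% or more.

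Two further objections stand as limits on the remedy. Coded reading leaves probe pressure, scan site and frame selection to a live operator who may know the method; for a compressible vein, pressure matters. Export and coding are also real work: whoever does them by hand sees the method, and a reader who acquired the scans may recognise some of them.

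**Conclusion.** The point holds in limited form. As written, the plan leaves a hand-placed outcome open to a reading bias that depends on the method, because nothing masks the post-warming readings and both the setting and the sequence reveal the method. That much follows from the text.

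How large the bias is cannot be learned from the documents. The calculated rates show how sensitive the comparison would be; they do not estimate what happened. They rest on the paired test, on the reading of d as a within-person effect, and on the assumed 0.1 to 0.3 SD range. Over that range the possible false-positive inflation is substantial, while the loss of power at the SAP's effect size is modest. Unmasked reading weakens confidence in the comparison without invalidating it. The change is worth making because it uses the study's own reader and alters neither sample size nor alpha.

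**What to change.** 1. State who applies each method, who scans and who measures.
2. Replace the post-warming step, and the matching baseline step, with acquiring and saving unannotated images of all three veins.
3. Export the images by an automated routine under random codes, with method, arm, occasion, time stamp and calipers hidden. The participant ID cannot serve as this code, because it does not conceal the method.
4. Have the study's own reader measure the coded images in random order. Lock the readings before the code is broken.
5. Use these readings in the analysis and keep the live readings as a sensitivity check.
6. If scanning is already finished, do this only if unannotated images or clips were saved. If they were not, report that the readings were unmasked as a limitation.

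**Cost.** Offline time for 1,224 readings, or 204 if masking is confined to one primary vein and axis, plus the work of export and coding. No additional reader or participant procedure is needed.

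**Limit.** This masks caliper placement only. Probe pressure, scan site and frame selection stay unmasked, and the fixed Airglove-then-WWI order is not addressed.

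### Airglove comes before warm water on the same arm with no reversal stated, so the method comparison cannot be separated from within-arm order and carry-over

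*Protocol*

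**What the plan says.** The Protocol's aim is to learn whether Airglove "dilates upper limb veins to the same degree as the warm water immersion (WWI) method".

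Under Design and Methods, the Procedure sets one sequence:

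- Before any warming: "Baseline 2D ultrasound long and short axis measurements of the dorsal metacarpal vein at the wrist", together with two veins at the elbow. This is the only baseline scan listed.
- Airglove: "Gently slide plastic sleeve onto RIGHT arm of volunteer, start machine". Three minutes of warm air, then a scan of the three veins.
- Rest: "Allow participants to rest 10 minutes before crossing to WWI method".
- WWI: "Immerse entire RIGHT forearm of the volunteer into the bucket for 3 minutes". The three veins are then scanned again.
- Other arm: "Repeat Airglove and warm water immersion procedures for participants LEFT arm". The methods are named in the same order, and no reversal is mentioned.

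The Procedure does not randomise or counterbalance the order, scan at the end of the rest, or give a reason for 10 minutes. The SAP covers sample size, software and the significance threshold. It has no order, period or carry-over term. It states: "This study enrolled 34 participants, a minimum sample size of 24 was required for 90% power".

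**The concern.** On the text as written, WWI is the second warming of an arm that was warmed shortly before. Method and position within the arm are then the same variable. The study has one comparison, and that comparison carries an extra term of unknown size and sign.

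The term could act either way:

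- **Additive residue.** If some Airglove dilatation remains after the rest, the WWI reading is raised. This favours WWI, and a result in which Airglove does at least as well would be conservative.
- **Capping.** If the vein is still near its maximum, the WWI response is limited. A real difference could then be hidden and the methods would look alike.

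The documents do not show which applies, and without a scan just before immersion the data cannot show whether any dilatation remained. A larger sample would not help: it makes the biased estimate more precise.

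**Working it through.** **Inputs.** Sequence, rest and baseline: Protocol, Procedure. Enrolled 34, minimum 24, power 90%, alpha 0.05, d = 0.833: SAP. The documents give no size for a period or carry-over effect and no SD of the paired difference, so those values are assumed below and shown as a range.

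**The plan's own figure.** At d = 0.833 and 90% power, t-based calculations give 18 (paired, two-sided), 14 (paired, one-sided), 32 per group (two-sample, two-sided) or 26 per group (two-sample, one-sided). None is exactly 24. This point does not depend on that figure; 24 and 34 are used only as sample sizes.

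**1. What the contrast estimates.** Let τ be the true WWI-minus-Airglove effect, δ the effect of being second on the arm, and λA and λW the carry-over left by Airglove and by WWI.

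- Airglove then WWI: WWI − Airglove = τ + δ + λA
- WWI then Airglove: WWI − Airglove = τ − δ − λW

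Current order on both arms: bias = δ + λA. One arm reversed: the average has bias (λA − λW)/2, so the period effect cancels and equal carry-overs cancel.

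**2. Whether a model can separate them.** Take the four post-warming measurements, with intercept, arm, within-arm period and method.

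| Order | Rank | Parameters |
|---|---|---|
| A-W on both arms | 3 | 4 |
| One arm reversed | 4 | 4 |

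Under the current order the method effect is not estimable once period is in the model.

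**3. Session-wide drift.** This is a lesser problem, because it also reaches the left-arm Airglove scan. With linear drift of one unit per measurement (times 1, 2, 3, 4):

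- A-W-A-W: (2 + 4)/2 − (1 + 3)/2 = 1.0 remains in the difference.
- A-W-W-A: (2 + 3)/2 − (1 + 4)/2 = 0. The mirror order also gives 0.

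With drift growing as time squared, A-W-A-W leaves (4 + 16)/2 − (1 + 9)/2 = 5. The two reversed orders leave −2 and +2, which cancel on average under randomisation.

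**4. Illustrative size.** The test is a two-sided 5% paired t-test with a mean shift b in SDs of the paired difference (noncentral t, noncentrality b√n). The SAP names no paired test; this is the one that fits the within-person design. With no true difference, the chance of a significant result is:

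| b | n = 24 | n = 34 |
|---|---|---|
| 0 | 5.0% | 5.0% |
| 0.1 | 7.6% | 8.7% |
| 0.2 | 15.6% | 20.5% |
| 0.3 | 29.1% | 39.7% |
| 0.5 | 65.0% | 80.8% |

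If d = 0.833 is read on the same scale (an assumption), shifts of 0.2, 0.3 and 0.5 are 24%, 36% and 60% of the planned effect (0.2/0.833, 0.3/0.833, 0.5/0.833).

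A shift can also mask a difference. With a true 0.833 in favour of Airglove and n = 34, the observable effect falls to 0.633, 0.533 or 0.333, and power falls from 99.7% to 94.8%, 85.5% or 47.0%.

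**5. What reversal achieves.** Assume δ = 0.1 and λA = 0.3, n = 34, SD of the difference held fixed.

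| Design | Bias | Significant with no true difference |
|---|---|---|
| Current order | 0.1 + 0.3 = 0.40 | 62% |
| Reversed, λW = 0.3 | 0 | 5% |
| Reversed, λW = 0.15 | 0.075 | 7% |
| Reversed, λW = 0 | 0.15 | 14% |

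With non-negative effects, reversal is worse only if (λW − λA)/2 > δ + λA, that is, λW > 3λA + 2δ.

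**6. Power cost.** For a period-adjusted two-sequence crossover with d = 0.833 as the paired effect, power is 97.4% at n = 24 and 99.7% at n = 34. The unadjusted paired t-test gives the same to one decimal.

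**The case against.** Five points can be made for the plan.

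- **The rest is a washout.** It may reduce carry-over, but nothing shows that 10 minutes is enough, and it does not deal with other effects of being second. It is a partial mitigation.
- **The left-arm order is not spelled out.** This stands: a reversal is unstated rather than ruled out. The natural reading is the same order, and the wording gives staff no reason to reverse.
- **The baseline scans help.** Also true. If both arms have a baseline, there are six measurements. A model with two arm levels, an Airglove effect, a WWI effect and linear time then has rank 5 of 5, so linear drift and a difference in vein size between arms are separable from method, provided the arms respond equally to warming. Adding same-arm carry-over gives rank 5 of 6. The drift problem shrinks; the carry-over problem does not.
- **The size is assumed.** This stands. The rejection rates show sensitivity and do not predict what happened in this study. At 0.1 SD the false-positive rate is only 8.7%.
- **Enrolment is described in the past tense.** If the 34 have all been measured, redesign is no longer possible and only the limitation statement remains. This changes which remedy applies. It does not make the comparison identifiable.

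**Conclusion.** The concern holds. On the natural reading of the Procedure, method is fully aliased with position within the arm, and the estimate carries a bias of δ + λA that no analysis of these data can remove. This part rests on the text and on algebra. It assumes only that the left arm follows the order in which the methods are named.

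The practical size is not known. Under assumed shifts of 0.1 to 0.5 SD of the paired difference, the false-positive rate at n = 34 runs from 8.7% to 80.8%; over 0.2 to 0.5 SD, power against a true 0.833 in favour of Airglove falls to between 94.8% and 47.0%. Either a finding of difference or a finding of similarity could come from order. This bears on the study's only aim, so it must be fixed if measurement is open and openly stated if it is not.

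**What to change.** **If data collection is open.** Use the reverse order on one arm and randomise, per participant, which arm starts with Airglove. Each participant then has Airglove-WWI-WWI-Airglove or its mirror. Analyse with method, period and arm terms, or average the within-arm differences over the two arms. The report should say that half the difference between the two carry-overs may remain.

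The cost is one protocol sentence and a randomisation list, with no extra participants or visits and almost no loss of power. The downside is having water ready at two different points in the session.

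**Optional.** Re-scan the three veins at the end of the rest and before the second warming. This would show residual dilatation directly, though not a capped response. It adds 6 vein scans to about 18 per participant (if baseline covers both arms). Whether they fit inside the rest is an assumption, because no scan duration is given. The Protocol says "Participants will expect to give up approximately 50 minutes to take part in the study", and warming and rests already take 4 × 3 + 2 × 10 = 32 of these (if each arm has one rest). The main change does not depend on the re-scan.

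**If the 34 were measured in the fixed order.** State in the report that method cannot be separated from within-arm order and carry-over, and limit the conclusion on equal dilatation accordingly. The cost is one limitation statement.
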